7.10 Randomization and numbering of subjects

An IXRS will be used for assigning eligible subjects to a treatment regimen based on a predetermined production randomization and/or packaging schedule provided by the CRO. The IXRS will generate individual assignments for subject kits of IMP, as appropriate, according to the visit schedule.

To enroll a subject (Screening), the Investigator or designee will contact the IXRS and provide brief details about the subject to be enrolled. Each subject will receive a 5-digit number assigned at screening that serves as the subject identifier throughout the study. The subject number will be required in all communication between the Investigator or designee and the IXRS regarding a particular subject. Subject numbers and kit numbers will be tracked via the IXRS.

The stratification for mNY classification will have the following 2 levels:

- mNY-positive
- mNY-negative

For enrollment in Part A, the IXRS will be designed to ensure that at least 45% and no more than 55% of the subjects belong to each of the 2 clinical subgroups above. Throughout the study, IXRS will be used for the calculation of ASDAS.

To randomize a subject (Week 48), the Investigator or designee will contact the IXRS and provide brief details about the subject to be randomized. The IXRS will automatically inform the Investigator or designee of the subject's randomization number. The IXRS will allocate kit numbers to the subject based on the subject number during the course of the study.

Randomization will be stratified on:

- Geographic region (North America, Western Europe, Eastern Europe, and Asia)
- mNY classification

In order to eventually end up with 210 subjects in sustained clinical remission qualifying for Part B, the enrollment will be adjusted accordingly. For such, the ASDAS will be monitored during Part A at various timepoints to predict the expected percentage of enrolled subjects responding well to the treatment and likely to achieve sustained remission at the end of Part A.

Subjects will be allocated to treatment during Part B in a 1:1:1 ratio (CZP 200mg Q2W: CZP 200mg Q4W: placebo).

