8.2 Baseline Visit (Week 0)

Subjects qualifying for this study will have the following procedures performed/recorded prior to study medication administration:

- Review of inclusion/exclusion criteria (The qualifying CRP levels from the Screening Period will be used for the inclusion criteria review at Baseline.)
- Vital signs (pulse rate, systolic and diastolic blood pressures, temperature and respiration rates)
- Blood samples will be collected for hematology, biochemistry analyses, serum calprotectin, and CRP
- Urine will be collected for urinalysis and for a urine pregnancy test for women of childbearing potential
- Physical examination (including extra-articular assessments, height, and weight)
- TB questionnaire

- BASMI and spinal mobility
- BASDAI
- BASFI
- SF-36
- ASQoL
- EQ-5D
- MASES
- Total spinal pain NRS and nocturnal spinal pain NRS
- Swollen and tender joint counts
- PtGADA
- PhGADA
- WPS
- Resources utilization
- IBD-Q
- Plasma sample for CZP concentration, ADAb
- Plasma sample for biomarkers, if applicable
- Genetics/epigenetics, proteomics if applicable
- Stool sample provided by the subject for fecal calprotectin evaluation
- Prior medications
- AEs
- Contact IXRS to randomize subject and to obtain kit number
- Study drug administration (after all other visit assessments are completed and laboratory samples are drawn)

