14.3 Planned efficacy analyses

14.3.1 Analysis of the primary efficacy variable

The primary efficacy variable is the proportion of subjects who do not experience a flare. The primary analysis will be based on logistic regression. The odds ratio based on the proportion of subjects who do not experience a flare will be estimated and tested between treatment groups using a logistic regression model with factors of treatment group, geographic region, and mNY criteria (yes/no). Geographic region and mNY classification are also randomization stratification factors. The use of region as a stratification variable and as a factor in the model is intended to combine study centers in similar geographic regions. The geographic regions to be used will be pre-defined in the IXRS and in the SAP. Each CZP dose will be compared against placebo to establish superiority over placebo and will be tested sequentially at an alpha of 0.05 as outlined in [Section 14.2](#).

An approach based on the principles of nonresponse imputation (NRI) will be used to impute missing values. Specifically, if a subject withdraws from Part B at any point, they will be considered as having not responded to treatment. Therefore, they will be assumed to have experienced a flare during Part B for analysis purposes. If a subject has an intermittent missing ASDAS score (ie, a missing value at 1 visit but nonmissing values at the previous and subsequent visit), then the missing value will be ignored and flare will be based on the 2 available values. If the ASDAS score is missing at 2 or more consecutive visits, then the subject will be treated as having experienced a flare (even if ASDAS scores are available after the missed visits).

Subgroup analyses based on age, gender, race, region, CRP level, ADA_b status, and mNY criteria will be performed. These analyses will be done for the primary efficacy variable and will be based on descriptive statistics only.

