14.3.2.2 Part B analysis

The time to flare will be analyzed using Kaplan-Meier methods. For those who meet the criteria for flare, the time will be defined as the length in days from randomization in Part B until the visit at which the criteria for flare were met. Subjects who discontinue the study without meeting the criteria for flare will be censored at the time of their last study visit. Subjects who complete the study without meeting the criteria for flare will be censored at their Week 96 visit. Between group differences will be analyzed with the log-rank statistic.

The changes from Baseline in ASDAS, BASDAI, BASFI, and BASMI at Week 96 for the RS will be compared between treatment groups using a mixed model for repeated measures (MMRM). The pattern of missingness for these variables is assumed to be missing at random (MAR). Subjects who enter Part B will have already demonstrated sustained remission through 48 weeks on CZP 200mg Q2W. Many of these subjects will be randomized to receive placebo and will, therefore, be more likely to experience a flare. Postflare data for subjects who experience a flare (in any treatment group) will be treated as missing for the MMRM analysis. It is further assumed that most subjects who discontinue at this late stage in the study (ie, during Part B) will do so as a result of reduced efficacy. Therefore, missing efficacy data due to either flare or study treatment discontinuation should be dependent on the observed efficacy scores, but independent of unobserved data.

The MMRM model will include Baseline score as a fixed-effect covariate, treatment group, region, mNY criteria (yes/no), and visit as fixed-effect categorical factors, and Baseline-by-visit and treatment group-by-visit as interaction terms. An unstructured correlation pattern will be used to estimate the variance-covariance of the within-subject repeated measures. Tables will present the adjusted means for placebo and the CZP doses (200mg Q2W and 200mg Q4W), the respective difference to placebo, the corresponding p-value, and 95% CI.

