Change from Baseline in SIJ SPARCC and spine ASpIMRI-a in the Berlin modification scores at Week 96 will be compared between treatment groups using analysis of covariance (ANCOVA) for observed values only (ie, no imputation). The model will include Baseline score, treatment group, region, and mNY criteria (yes/no). Tables will present the adjusted means for placebo and the CZP doses (200mg Q2W and 200mg Q4W), the respective difference to placebo, the corresponding p-value, and 95% CI.

The binary secondary efficacy variables (ASDAS-MI, ASDAS-CII, ASAS20, ASAS40, ASAS5/6, ASAS PR, and BASDAI50 response) at Week 96 will be analyzed using a logistic regression. The odds ratio of the responder rates at Week 96 will be estimated and tested

between treatment groups using a logistic regression model with factors of treatment group, region, and mNY criteria (yes/no). Tables will present the responder rates for placebo, CZP 200mg Q2W, and CZP 200mg Q4W, the respective effect estimates (adjusted odds ratio with reference to placebo), p-values, and 95% CIs. Subjects with a missing responder status at Week 96 will be treated as a nonresponder for analysis purposes (ie, NRI).

Ankylosing Spondylitis Disease Activity Scores (ASDAS-ID, ASDAS-MD, ASDAS-HD, ASDAS-vHD) will be summarized by treatment group using summary statistics (counts and percentages) based on observed case data.

In addition to the analyses mentioned above, descriptive statistics (number of available observations [n], mean, median, SD, minimum, and maximum) will be provided by treatment group for the secondary efficacy variables. The descriptive analyses will be covered in the tables summarizing the variables over time. This will include a summary of the actual values, change from Baseline (Week 0), and change from randomization Baseline (Week 48). The statistical comparisons described for secondary efficacy variables are not part of the multiplicity-controlled testing procedure described in [Section 14.2](#). The p-values reported for these analyses will not be adjusted for multiplicity and will be considered nominal. All analyses and summaries of secondary efficacy variables in Part B will be based on the RS.

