14.3.3.2 Part B

Treatment group comparisons for both CZP groups vs placebo will be performed based on the change from Baseline in other selected efficacy variables. These analyses will be performed using an ANCOVA model with variables of Baseline score, treatment group, region, and mNY criteria (yes/no) in the model. The treatment differences and corresponding 95% CIs will be calculated based on the adjusted means. Missing values will be imputed using LOCF. This analysis approach will be used for the following variables:

- Total spinal pain
- Nocturnal spinal pain
- PtGADA
- Morning stiffness (BASDAI 5 and 6)
- SF-36 PCS, MCS, and physical function domain
- Fatigue NRS
- ASQoL

Such analyses will also be done for the following continuous variables: ASDAS, BASDAI, BASFI, and BASMI will be analyzed using a MMRM similar to the one specified in [Section 14.3.2.2](#) at timepoints not covered in the secondary efficacy analyses. Additionally, ASDAS-MI, ASDAS-CH, ASAS, and BASDAI50 response variables will be analyzed using a logistic regression model similar to the one specified for binary response variables in [Section 14.3.2.2](#) at timepoints not covered in the secondary efficacy analyses.

These comparisons are not part of the multiplicity-controlled testing procedure described in [Section 14.2](#). The p-values reported for these analyses will not be adjusted for multiplicity and will be considered nominal. Exploratory statistical comparisons will also be performed for WPS scores using the nonparametric bootstrap-t method. This will be explained in greater detail in the SAP.

All other efficacy variables will be summarized descriptively by visit and treatment group using observed case and imputed data based on the RS.

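### The score-adjusted Part B models use only the Week 0 score as score covariate and leave out the Week 48 score taken at randomisation, which gives up precision but causes no bias

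*Protocol*

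**What the plan says.** For the continuous secondary variables at Week 96, Section 14.3.2.2 sets out the repeated-measures model: "The MMRM model will include Baseline score as a fixed-effect covariate, treatment group, region, mNY criteria (yes/no), and visit as fixed-effect categorical factors", together with Baseline-by-visit and treatment-by-visit interactions. For the sacroiliac and spinal MRI scores the same section uses ANCOVA on observed values: "The model will include Baseline score, treatment group, region, and mNY criteria (yes/no"). Section 14.3.3.2 compares the other selected continuous variables "using an ANCOVA model with variables of Baseline score, treatment group, region, and mNY criteria (yes/no) in the model".

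Baseline means Week 0. The visit section is headed "8.2 Baseline Visit (Week 0"), and Section 14.3.2.2 keeps the two timepoints apart when it lists its descriptive summaries: "change from Baseline (Week 0), and change from randomization Baseline (Week 48"). Randomisation comes 48 weeks after Baseline. Section 7.10 says: "To randomize a subject (Week 48), the Investigator or designee will contact the IXRS".

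The Week 48 values exist. Section 8.3.2 collects CRP, BASDAI, BASFI, SF-36, ASQoL, the spinal pain scales and PtGADA 3 to 5 days before the Week 48 visit, and Section 14.2 makes the laboratory and tablet data from that time the Week 48 values. Section 8.3.1 schedules BASMI and MRI at Week 48. In the analysis they appear only descriptively, as change from the randomisation baseline.

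**The concern.** The arms come into being at Week 48, among subjects selected for sustained remission. At Screening the same subjects had to have active disease (ASDAS at least 2.1, BASDAI at least 4; Section 6.1). The Week 0 score therefore describes a different disease state, 48 weeks before allocation, and may say little about Week 96. The score closest to randomisation is the natural covariate for a comparison that starts there. It accounts for chance differences between arms at allocation, and it removes outcome variance to the extent that it predicts Week 96 beyond what Week 0 already explains. At stake are the width of the intervals and the stability of the estimated differences for the continuous Part B variables, with a planned 70 subjects per arm.

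**Working it through.** **The plan's own figure.** The protocol states no power or precision for these continuous comparisons. Its only power figures are 98% and 94% for the primary no-flare comparison (Section 14.8: 70 per arm; 80%, 75% and 45%; two-sided 0.05). They reproduce: 99.4% and 96.0% with a pooled-variance normal approximation, 98.9% and 94.0% with Fisher's exact test. They do not depend on the present point, because the primary model carries no score covariate: "using a logistic regression model with factors of treatment group, geographic region, and mNY criteria (yes/no").

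**Inputs.** From the protocol: 70 per arm. Assumed, because the protocol gives no correlations or SDs: r(0,48) = 0.3; r(0,96) from 0.1 to 0.4; r(48,96) from 0.3 to 0.7; complete data; Week 96 SD scaled to 1.

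**Step 1: the outcome scale does not matter.** With the Week 0 score in the model, change from Week 0 gives the same treatment contrast as the Week 96 value. With both scores in the model, the contrast is the same for change from Week 0 and change from Week 48. So the question concerns residual variance only.

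**Step 2: residual variance.**
- Week 0 only: 1 − r(0,96)².
- Both scores: 1 − R², with R² = [r(0,96)² + r(48,96)² − 2·r(0,96)·r(48,96)·r(0,48)] / [1 − r(0,48)²].

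| Case | r(0,96) | r(48,96) | Week 0 only | Both | Ratio | 70 per arm is worth |
|---|---|---|---|---|---|---|
| Weak | 0.4 | 0.3 | 0.840 | 0.804 | 0.96 | about 73 |
| Middle | 0.2 | 0.5 | 0.960 | 0.747 | 0.78 | about 90 |
| Strong | 0.1 | 0.7 | 0.990 | 0.497 | 0.50 | about 140 |

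Middle case in full: R² = (0.04 + 0.25 − 0.06)/0.91 = 0.253; 0.747/0.960 = 0.778; standard error ratio √0.778 = 0.88; 70/0.778 = 89.9. For an assumed true difference of 0.5 SD, power goes from 85.5% to 92.8%.

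**Step 3: chance imbalance.** The difference between two arm means at Week 48 has SD √(2/70) = 0.17 SD units, so a 95% range of about ±0.33. It reaches the Week 96 contrast only through the partial slope of Week 96 on Week 48 given Week 0. In the middle case that slope is (0.5 − 0.2 × 0.3)/0.91 = 0.48. The part of the imbalance that Week 0 does not explain has SD 0.169 × √0.91 = 0.161. The contribution to the contrast therefore has SD 0.48 × 0.161 = 0.08. This is the same quantity as the variance saving in Step 2, not an additional loss.

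**Step 4: add or replace.** Replacing Week 0 by Week 48 gives ratios from 0.52 to 1.08. The loss occurs where Week 0 is the better predictor (0.4 against 0.3: 0.91/0.84 = 1.08). Adding Week 48 lowers the residual variance in every case examined.

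**The case against.** The strongest defence is that nothing here is wrong or inconsistent. The endpoint in Section 4.1.2.2 is change from Baseline, the covariate is the matching Baseline score, and Week 0 precedes randomisation. Randomisation keeps the contrast unbiased, and the intervals already allow for chance imbalance at Week 48. That stands: the point is about efficiency, not validity.

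Several stronger readings are tempting, and the protocol does not support them.
- A reader might infer that all randomised comparisons in Part B are affected. The primary logistic model, the log-rank test and the binary secondary models contain no score covariate at all. The score-adjusted models also include region and mNY status.
- A reader might infer that a Week 48 imbalance enters the treatment difference in full. It enters only through the partial slope of Step 3.
- A reader might infer that the Week 48 score is ignored altogether. Change from Week 48 is a listed Part B variable (Section 4.1.3.2) and is tabulated by arm, so an imbalance would be visible. It is absent from the models only.

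It is also fair to say that the size rests wholly on assumed correlations, and that the formula holds for complete data whereas post-flare values are set to missing in the MMRM. Entry requires ASDAS below 1.3 at Week 48 (Section 3), which restricts the range of that score. BASDAI is restricted indirectly, since three of its items enter ASDAS (Section 9.1.7). Both limit the gain.

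Leaving the matter to the SAP is a weaker defence, because the protocol itself lists what the models will contain.

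**Conclusion.** The point holds as an avoidable loss of precision in the continuous, score-adjusted Part B analyses: the MMRM for ASDAS, BASDAI, BASFI and BASMI, the MRI ANCOVA, and the ANCOVAs of Section 14.3.3.2. These carry nominal p-values outside the multiplicity procedure, so no confirmatory conclusion and no stated power figure changes. Over the assumed correlations, between about 4% and 50% of the complete-data residual variance could be removed, and 22% in the middle case. The gain is probably small for ASDAS. BASFI, BASMI and MRI are not restricted directly by the entry rule, but nothing in the protocol shows how large their gain would be. The reading of the models is certain; the size of the gain is not.

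**What to change.** In Sections 14.3.2.2 and 14.3.3.2, add the last pre-randomisation (Week 48) score of the variable analysed to the MMRM and to each ANCOVA, with its by-visit interaction in the MMRM. Keep the Week 0 score. Use only post-randomisation visits as outcomes, so that Week 48 is not both covariate and response. The endpoint, change from Week 0, stays as it is.

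MRI needs a safeguard. Table 5.1 and Section 8 allow the Week 48 scan a window of ±2 weeks, while randomisation and the first Part B dose fall at the Week 48 visit, so some scans may follow randomised treatment. Use the scan as covariate only if it was taken before that dose. Because this ANCOVA is on observed values, state how a missing pre-dose scan is handled so that nobody is dropped, for example covariate mean imputation with a missing indicator.

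The cost is one covariate per model, prespecified before unblinding. No new data are needed.

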2.5 Rationale

The demonstration of maintenance of response after reduction or even withdrawal of treatment would offer the physician and patient the opportunity to minimize the risks of anti-tumor necrosis factor (TNF) treatment while reducing healthcare costs. The data available to date suggest that anti-TNF therapy withdrawal in patients with active, nonradiographic, and/or early axSpA who are either in remission, or who have an ASAS40 response resulted in a flare (defined as loss of sustained remission, loss of ASAS40 response, or BASDAI >3 at 2 consecutive visits) in the majority (56 to 83%) of patients, resulting in the need to re-establish treatment (Haibel et al, 2013; Sieper et al, 2013a; Song et al, 2012). Publications that reported the effects of retreatment after a flare indicated that, in general, patients flaring responded well to retreatment. However, these studies did not provide information on questions such as whether there is an increased risk of immunogenicity following retreatment.

Available data suggest that the efficacy of anti-TNF treatment can be maintained even with reduction in dosage in a majority of patients with AS (Cantini et al, 2013; Olivieri et al, 2013). However, these studies suffer from several limitations and therefore there is a need to generate further robust data from prospective placebo-controlled, randomized studies to address the question of whether and in which patients dose reduction can be considered.

The AS0005 study introduces both a full withdrawal arm (placebo) as well as a half-dose arm (CZP 200mg Q4W) to assess a potential differential effect between both active treatment arms (full-dose and half-dose) and placebo. Furthermore, it will also provide data on the efficacy and safety of retreatment after subjects experience a flare in disease activity.

The treatment of axSpA with TNF-inhibitors is known to also have some beneficial impact on extra-articular manifestations, like uveitis, psoriasis, and IBD. AS0005 will provide data on the

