Subjects experiencing a flare in Part B will be invited for an onsite visit to receive the next planned dose of investigational product (escape treatment). This visit will take place 2 weeks after the last assessment that resulted in meeting the flare criteria; or, at the discretion of the Investigator, at an earlier timepoint. As the start of escape treatment may vary from subject to subject, it will be referred to as “Escape Week 0” in [Table 5.2](#). Subjects will remain on the escape treatment for at least 12 weeks or until Week 96 of the regular visit schedule as described in [Table 5.1](#), whichever is longer.

The assessment schedule for subjects experiencing a flare in Part B will start 2 weeks after the flare condition is confirmed and will end 2 weeks before Week 96 after Baseline of the regular assessment schedule ([Table 5.2](#)). If the flare occurs late in Part B (at or after Week 82), the subject must receive the escape treatment for 12 weeks (eg, starting at Week 84 until Week 96). The final assessments at study end (as laid down for Week 96) must be performed 2 weeks after the last study dose administration ([Table 5.1](#)).

Table 5.2: Schedule of study assessments for all subjects experiencing a flare in Part B

Study-Period	Part B for subjects experiencing a flare						
	3B						
Visit / week (W) on escape treatment	0	2	4	6 to 10 H/H N ^a	12 (and every 12 weeks thereafter) ^b	every 2 weeks in between ^c H/HN ^a	
Vital signs ^d	X	X	X		X		
Hematology/urine/ biochemistry	X				X		
CRP ^e	X	X	X	X ^f	X		X ^f
Stool sample ^g	X				X		
Serum calprotectin ^g	X				X		
IBD-Questionnaire ^g	X				X		
PE	X	X	X		X		
Extra-articular assessments	X		X		X		
MRI ^h	X				X		
TB questionnaire	X				X		
BASMI & Spinal mobility ⁱ	X	X	X		X		
BASDAI	X	X	X	X ^f	X		X ^f
BASFI	X	X	X		X		
SF-36	X		X		X		
AsQoL	X	X	X		X		
EQ-5D	X		X		X		

Table 5.2: Schedule of study assessments for all subjects experiencing a flare in Part B

Study-Period	Part B for subjects experiencing a flare						
	0	2	4	6 to 10 H/H N ^a	12 (and every 12 weeks thereafter) ^b	every 2 weeks in between ^c H/HN ^a	3B
Visit / week (W) on escape treatment							
Protocol Activity							
MASES	X	X	X			X	
Total and nocturnal spinal pain	X	X	X			X	
Patient's Global Assessment of Disease Activity	X	X	X	X ^f		X	X ^f
Physician's Global Assessment of Disease Activity	X	X	X			X	
Work Productivity Survey	X		X			X	
Resources utilization ^j	X		X			X	
CZP plasma concentration/ADAb	X	X	X			X	
Biomarker	X	X	X			X	

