14.4 Planned safety and other analyses

14.4.1 Safety analyses

The frequency of all AEs by study period (Part A and Part B) will be presented separately by System Organ Class, high-level term, and preferred term and for Part B by each treatment group. The data will be displayed as number of subjects experiencing the AEs, percentage of subjects, and number of AEs. Data will also be corrected for exposure by 100 patient years.

Laboratory evaluations and vital signs will be analyzed over time in the SS and SSB for observed cases and at the end of treatment.

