14.6 Handling of dropouts or missing data

For the primary efficacy variable (percentage of subjects in Part B who do not experience a flare), an approach based on the principles of NRI will be used to impute missing values. Specifically, if a subject withdraws from Part B at any point, they will be considered as having not responded to treatment. Therefore, they will be assumed to have experienced a flare during Part B for analysis purposes. If a subject has an intermittent missing ASDAS score (ie, a missing value at 1 visit but nonmissing values at the previous and subsequent visit), then the missing value will be ignored and flare will be based on the 2 available values. If the ASDAS score is missing at 2 or more consecutive visits, then the subject will be treated as having experienced a flare (even if ASDAS scores are available after the missed visits).

For the time to flare endpoint, the rules as described above for the primary endpoint will be applied to account for missing data when determining whether or not a subject experienced a flare. Subjects who discontinue the study without meeting the criteria for flare will be censored

at the time of their last study visit. Subjects who complete the study without meeting the criteria for flare will be censored at their Week 96 visit.

Selected continuous secondary efficacy variables will be analyzed using MMRM methods (see [Section 14.3.2.2](#) for details). Missing data for binary response secondary efficacy variables will be handled using NRI. Secondary variables related to MRI will be analyzed based on the observed case data.

In general, other efficacy variables will be summarized as both observed case and with imputation (NRI for binary response variables and LOCF for continuous variables), unless otherwise specified. Nonresponse imputation is implemented by treating missing data for binary response variables as a nonresponse. The LOCF summaries will impute missing continuous data using the last post-Baseline nonmissing result. In the event that a subject has no post-Baseline data for a given continuous variable, no imputation will be performed.

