14.8 Determination of sample size

It is anticipated that approximately 210 subjects will be randomized in a 1:1:1 ratio to the CZP 200mg Q2W, CZP 200mg Q4W, and placebo treatment groups. The primary efficacy analysis is based on the proportion of subjects who do not experience a flare during Part B of the study. The proportion of subjects who do not experience a flare during Part B is assumed to be 80%, 75%, and 45% for the CZP 200mg Q2W, CZP 200mg Q4W, and placebo treatment groups, respectively. Given these assumptions, a sample size of 70 subjects per group provides 98% power to detect a significant difference between the CZP 200mg Q2W dose and placebo and 94% power to detect a significant difference between the CZP 200mg Q4W dose and placebo using a 2-sided significance level of 0.05.

Given that subjects enter Part B only if they have achieved sustained remission in Part A, it is necessary to estimate the number of subjects needed to enroll in Part A. It is assumed that approximately 28% of subjects enrolled in Part A will achieve sustained remission and qualify for Part B. This means that about 750 subjects will be enrolled in Part A in order to have 210 subjects who are randomized into Part B. Subject response to treatment will be evaluated on an ongoing basis as subjects enroll in Part A, and the number of subjects enrolled will be adapted accordingly in order to achieve 210 subjects randomized to Part B.

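### Of the Part B secondary and other efficacy analyses that use data collected after a flare, only the MMRM excludes them; the rest score full-dose retreatment results under the randomised arm

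*Protocol*

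**What the plan says.** After a flare, placebo and half-dose subjects receive full-dose CZP until the end of the Double-Blind Period or for at least 12 weeks, whichever is longer (protocol Sections 5.1.3 and 6.3.2). They still have the Week 96 assessments (Table 5.2, note b; Section 8.5), so their Week 96 status is normally observed.

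The Part B efficacy rules then differ by analysis:

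- **MMRM for ASDAS, BASDAI, BASFI and BASMI** (Section 14.3.2.2): "Postflare data for subjects who experience a flare (in any treatment group) will be treated as missing for the MMRM analysis".
- **Week 96 logistic regressions** for ASDAS-MI, ASDAS-CII, ASAS20, ASAS40, ASAS5/6, ASAS PR and BASDAI50 (Section 14.3.2.2): "Subjects with a missing responder status at Week 96 will be treated as a nonresponder for analysis purposes (ie, NRI". Section 14.6 likewise defines NRI by missing data alone.
- **ASDAS disease activity categories and the MRI ANCOVA** (Section 14.3.2.2): observed data only, with no mention of flare.
- **ANCOVAs for spinal pain, PtGADA, morning stiffness, SF-36, fatigue and ASQoL** (Section 14.3.3.2): "Missing values will be imputed using LOCF". Section 14.6 adds: "The LOCF summaries will impute missing continuous data using the last post-Baseline nonmissing result".

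Section 14.3.2.2 bases the Part B secondary analyses on the Randomized Set, which includes flared subjects. Section 14.2 says the same of Part B efficacy analyses in general.

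**The concern.** The protocol recognises in Section 14.3.2.2 that data gathered after a flare no longer reflect the randomised regimen, and then limits the remedy to one model. The same placebo subject who flares, escapes and recovers is a failure in the primary analysis, missing after the flare in the MMRM, and an observed placebo responder in the Week 96 logistic regressions.

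The arms differ sharply in how many subjects this touches, so the effect is to pull the arms together. It is also expected: Section 2.5 reports from earlier withdrawal studies that "in general, patients flaring responded well to retreatment". Published Week 96 odds ratios could then suggest that dose reduction or withdrawal costs little, when what they partly measure is success of retreatment. This is not a detail simply left to the SAP, because the protocol names the imputation rule for each analysis. An SAP that follows those rules literally reproduces the gap.

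**Working it through.** **Inputs from the protocol (Sections 7.10 and 14.8).** 1:1:1 allocation, 70 per arm, two-sided alpha 0.05. Assumed flare-free proportions f: 80% (Q2W), 75% (Q4W), 45% (placebo). Stated power: 98% for Q2W and "94% power to detect a significant difference between the CZP 200mg Q4W dose and placebo using a 2-sided significance level of 0.05".

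**Step 1: reproduce the stated power.** For two proportions with pooled variance under the null,

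power = Φ{[d − 1.96·√(2p̄(1−p̄)/70)] / √[(p₁(1−p₁)+p₂(1−p₂))/70]}.

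For 80% vs 45%: d = 0.35 and p̄ = 0.625, so (0.35 − 0.160)/0.0763 = 2.49, which gives 99.3%. For 75% vs 45% the result is 96.0%. Variants:

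- continuity-corrected: 98.9% and 94.1%
- Wald log odds ratio: 98.5% and 94.4%
- exact Fisher: 98.9% and 94.0%

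The stated 98% and 94% are therefore reproduced to within method differences. They concern the primary endpoint.

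**Step 2: how many subjects are affected.** Under the same rates, flare (or another failure counted as flare) occurs in 0.55 × 70 = 38.5 placebo, 0.25 × 70 = 17.5 half-dose and 0.20 × 70 = 14 full-dose subjects.

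**Step 3: Week 96 responder rate as the text stands.** Let q be the response rate among non-flared subjects and r the Week 96 response rate among flared subjects, the same in all arms. Each arm's rate is f·q + (1−f)·r. The difference from placebo is then

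- Q2W: (0.80 − 0.45)(q − r) = 0.35(q − r)
- Q4W: (0.75 − 0.45)(q − r) = 0.30(q − r)

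The protocol gives neither q nor r; both are assumptions. With q = 1 and no withdrawals:

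| r | Q2W / Q4W / placebo, % | Q2W − placebo, points (power) | Q4W − placebo, points (power) |
|---|---|---|---|
| 0 (flare = nonresponse) | 80 / 75 / 45 | 35 (99%) | 30 (96%) |
| 0.3 | 86 / 82.5 / 61.5 | 24.5 (92%) | 21 (80%) |
| 0.5 | 90 / 87.5 / 72.5 | 17.5 (76%) | 15 (60%) |
| 0.7 | 94 / 92.5 / 83.5 | 10.5 (50%) | 9 (37%) |
| 0.9 | 98 / 97.5 / 94.5 | 3.5 (19%) | 3 (15%) |

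**Step 4: sensitivity.**

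- *Withdrawals.* If 20% of the assumed failures withdraw and become nonresponders by NRI, then at q = 1 and r = 0.7 the differences are 0.912 − 0.758 = 15.4 points (69%) and 0.890 − 0.758 = 13.2 points (54%). The dilution is smaller but remains.
- *Imperfect response without flare.* At q = 0.9 with no withdrawals, the Q2W − placebo difference falls from 31.5 points (97%) at r = 0 to 14 points (48%) at r = 0.5, 7 points (19%) at r = 0.7 and zero at r = 0.9.

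No comparable figure can be computed for the MRI, ASDAS category or LOCF analyses, because the protocol gives no means or variances for them.

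**The case against.** The strongest reply is that analysing Week 96 status in all randomised subjects regardless of escape is a legitimate treatment-policy question. It differs from the flare question without contradicting it, and retreatment has its own Flared Set tables. The first part stands as a principle, but the protocol does not present these analyses that way, and the MMRM beside them, on the same subjects, does the opposite. As for the Flared Set, the sentence in Section 14.3.2.3 assigns post-flare summaries to that set. It does not remove those data from the Randomized Set analyses.

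It is also true that the consequence is limited. Sections 14.3.2.2 and 14.3.3.2 place these comparisons outside the multiplicity-controlled procedure, with nominal p-values. The primary endpoint and time to flare are settled at the flare and do not change.

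Four stronger readings are tempting but not supported:

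- *The placebo comparison would reverse.* With a common r the difference is 0.35(q − r), which is negative only if flared subjects respond better than non-flared ones. Otherwise, reversal needs full-dose flarers to do markedly worse than escapers. That is conceivable, since their dose does not change, and it would deepen the dilution. But the protocol gives no rate for either group.
- *Part B adverse events are wrongly credited to placebo.* Section 14.4.1 says only "preferred term and for Part B by each treatment group". It does not say whether that means randomised or received treatment, and Section 14.1 defines a Full-Dose Set that includes escape treatment. Attribution is left open, not misstated.
- *A final visit later than Week 96 after a late flare is an error.* Section 5.2 provides for it openly: "The final assessments at study end (as laid down for Week 96) must be performed 2 weeks after the last study dose administration". It is a design feature.
- *LOCF ANCOVA must give way to the MMRM.* That is a preference of method. The point here is which values LOCF may carry.

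**Conclusion.** The point holds for efficacy. Among the Part B secondary and other efficacy analyses that would use data collected after a flare, the MMRM alone excludes them. Read literally, the Week 96 logistic regressions, the observed-case ASDAS categories, the MRI ANCOVA and the LOCF ANCOVAs credit retreatment results to the placebo and half-dose arms.

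For the responder endpoints the bias runs toward no difference from placebo. The size in the table rests on the protocol's 80/75/45% rates plus three assumptions of this review: every non-flared subject responds, nobody withdraws, and flared subjects in all arms share one response rate. Withdrawals handled by NRI would lessen the effect. The figures are illustrations and not predictions. Because the affected p-values are nominal and the primary result is untouched, this should be fixed but is not critical to the trial's main conclusion.

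**What to change.** In Sections 14.3.2.2, 14.3.3.2 and 14.6, state one post-flare rule, in line with that of the MMRM, for every Part B efficacy comparison on the Randomized Set, in all treatment groups:

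- **Binary variables:** from the flare on, the subject is a nonresponder.
- **ASDAS categories, MRI and continuous variables:** post-escape values are not used, and LOCF must not carry a value from the escape period.
- **Retreatment results:** report them in the Flared Set tables. Any Randomized Set analysis that includes post-escape data is an additional one, labelled treatment-policy.

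One detail needs wording. SF-36 and ASQoL are first scheduled in Part B at Week 60 (Section 8.3.1), so a subject who flares earlier has no Part B value before the flare, and LOCF would reach back to Part A. The text should say whether the Escape Week 0 assessment, which Section 8.5 places before that visit's dose, may be used.

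The cost is wording and programming, with no new data collection, and the change should be made before unblinding. Week 96 responder rates will fall in all arms, and fewer observed MRI values will enter that comparison.
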